## **5. ANALYSIS SETS**

Analysis populations are defined for per-protocol (PP) efficacy, modified intent-to-treat (mITT) efficacy, safety, mITT immunogenicity, and mITT colonization.

### **5.1. Modified Intent-to-Treat Efficacy Populations**

To be included in the mITT efficacy population, a subject must be vaccinated and undergo spinal surgery. Subjects will be assigned to the investigational product to which they were randomized (SA4Ag or placebo).

Subjects who do not undergo spinal surgery following vaccination will not be included in the mITT efficacy population. If any efficacy data are collected in these subjects, it will be listed separately.

A subset of the mITT efficacy population, referred to as the restricted mITT efficacy population, will also exclude subjects with a pre-existing infection, or malignancy, or acute or emergency trauma, at any time from enrollment up to and including the time of the index surgery. This population will be used for selected efficacy analyses only (see [Section 8.2.1](#)).

### **5.2. Per-Protocol Efficacy Population**

To be included in the PP efficacy population, a subject must:

- meet all eligibility criteria,
- be vaccinated as randomized,
- undergo the index surgery 9 to 90 days (inclusive) after vaccination (this is expanded from 10 to 60 days as stated in the protocol, which represents a more restricted window with the aim of ensuring the per-protocol population timeframe used in the analyses is respected),
- undergo surgery consistent with study-defined criteria for the index surgery,

- not have the index surgery modified to be a staged procedure on separate days,
- have no major protocol violations before reporting of the suspected *S aureus* infection, and
- have no infection or malignancy identified at the index surgical procedure.

Because of confidentiality requirements in Germany, only year of birth can be provided; therefore, the date of birth will be reported as 01 July of the year of birth. Thus, ordinary age calculations might flag a subject as outside the permitted age range of 18 to <86 years. Subjects from Germany who enroll before 01 July and have a calculated age of 17 years may still be included in the PP efficacy population if all other criteria are fulfilled.

Subjects from Germany who enroll after 01 July and have a calculated age of 86 years may still be included in the PP efficacy population if all other criteria are fulfilled.

Subjects will be assigned to the investigational product to which they were randomized (SA4Ag or placebo).

### **5.3. Safety Population**

All subjects who receive investigational product will be included in the safety population. Subjects will be assigned to the investigational product they actually received.

### **5.4. Other Populations**

#### **5.4.1. mITT immunogenicity population**

The mITT immunogenicity population comprises all subjects who were vaccinated and have at least 1 valid and determinate post-vaccination immunogenicity result. Subjects are assigned to the investigational product that they are randomized to.

#### **5.4.2. mITT Colonization Population**

The mITT colonization population includes all randomized subjects who had at least 1 valid colonization swab sample result.

### **5.5. Vaccine Group Misallocations**

Subjects who are randomized but receive the wrong investigational product will be included under their randomized vaccine group for mITT efficacy, mITT immunogenicity, and mITT colonization analyses, but will be included in the group for the investigational product they actually received for safety analyses.

Subjects who receive SA4Ag or placebo but do not undergo index surgery will be included in the safety analyses, but will be excluded from all efficacy, immunogenicity, colonization, and healthcare utilization analyses.

## 5.6. Protocol Deviations

The following protocol deviations will exclude affected subjects from the indicated populations:

### 5.6.1. Protocol Deviations Occurring Before Randomization

Subjects who do not meet all eligibility criteria will be excluded from the PP efficacy population.

### 5.6.2. Protocol Deviations Occurring After Randomization

1. Vaccinated subjects who do not undergo the planned index surgery will be included only in the safety population.
2. Nonvaccinated subjects will be excluded from all populations.
3. Subjects will be excluded from the PP efficacy population for any of the following reasons:
  - a. Not vaccinated as randomized
  - b. Undergoing index surgery 8 days or sooner after vaccination *or* 91 days or later after vaccination
  - c. Not meeting 1 or more of the study-defined criteria for the index surgery
  - d. Having 1 or more major protocol deviations expected to affect efficacy or immunogenicity, prior to the onset date of suspected *S aureus* infection as determined by a medically qualified clinician at the sponsor
  - e. Suspected or confirmed infection or malignancy identified during the index surgical procedure

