9.3.1. Efficacy Analysis Populations

Two analysis populations are defined: per-protocol and mITT. To be included in the per-protocol efficacy population, a subject must meet all eligibility criteria, be vaccinated as randomized, undergo the index surgery 10 to 60 days after vaccination, undergo surgery consistent with study-defined criteria for the index surgery, have no major protocol violations prior to reporting of the suspected *S aureus* infection, and have no infection or malignancy identified at the index surgical procedure. To be included in the mITT population, a subject must be vaccinated and undergo spinal surgery. For both populations, subjects will be assigned to the investigational product to which they were randomized (SA4Ag or placebo).

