### 2.1. Study Design

*This is a Phase 2b, multicenter, parallel-group, placebo-controlled, randomized, double-blind study to evaluate Staphylococcus aureus 4-antigen vaccine (SA4Ag) safety and efficacy in the prevention of postoperative S aureus disease in adults aged 18 to <86 years who are undergoing elective open posterior instrumented spinal fusion procedures with multilevel instrumentation.*

This is an event-driven study with a total target of 48 primary endpoint *S aureus* cases; it is anticipated that approximately 6,000 subjects will be enrolled globally to accumulate these 48 cases. However, the total enrollment number may vary based on the incidence rate of the primary endpoint, true underlying vaccine efficacy (VE), and potential early study stop for efficacy or futility.

*There are 5 scheduled study visits and 1 scheduled telephone contact during 6 to 8 months of subject participation. Study-eligible subjects who provided consent will be randomized in a 1:1 ratio to receive a single dose of SA4Ag or placebo at Visit 1, which occurs 10 to 60 days prior to undergoing elective open posterior instrumented spinal fusion procedures with multilevel instrumentation (index surgical procedure). Visit 2 is a longitudinal visit and is to monitor the index hospital admission period from the day of surgery (Day 1) until the day of discharge. A telephone contact with the subject will occur on Day 21, while postoperative evaluation study visits will occur on Day 42, Day 90, and Day 180 after surgery.*

*Following the index hospital admission, unscheduled visits will be conducted for assessment of suspected bloodstream infection (BSI) and/or surgical-site infection (SSI) events, and to assess hospitalization(s) subsequent to the index hospital admission.*

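### SAP 5.6.2(1) keeps vaccinated subjects without the planned index surgery out of mITT, although SAP 5.1 and Protocol 9.3.1 admit any spinal surgery; SAP 5.5 is ambiguous on the same point

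*SAP*

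**What the plan says.** Two sections define mITT efficacy in the same way.

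- Protocol 9.3.1: "To be included in the mITT population, a subject must be vaccinated and undergo spinal surgery".
- SAP 5.1: "To be included in the mITT efficacy population, a subject must be vaccinated and undergo spinal surgery". SAP 5.1 also gives the exclusion: "Subjects who do not undergo spinal surgery following vaccination will not be included in the mITT efficacy population".

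Two other SAP sections allocate subjects by index surgery.

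- SAP 5.6.2, item 1: "Vaccinated subjects who do not undergo the planned index surgery will be included only in the safety population".
- SAP 5.5: "Subjects who receive SA4Ag or placebo but do not undergo index surgery will be included in the safety analyses", but these subjects "will be excluded from all efficacy, immunogenicity, colonization, and healthcare utilization analyses". This text does not contain the word *planned*.

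SAP 2.1 defines the index procedure narrowly: "elective open posterior instrumented spinal fusion procedures with multilevel instrumentation (index surgical procedure". SAP 5.6.2, item 3c, lists "Not meeting 1 or more of the study-defined criteria for the index surgery" among the reasons for leaving the per-protocol efficacy population. Protocol 6.1 keeps subjects whose surgery did not follow the index definitions in all study procedures.

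**The concern.** The operation a subject actually has is settled after randomization. The mITT analyses are there to show whether the per-protocol exclusions matter, and type of surgery is one of those exclusions. If item 1 is programmed as written, mITT can no longer show what that particular exclusion does.

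There is also a reproducibility problem. Two programmers could build different mITT sets from the same SAP, one from 5.1 and one from 5.6.2. The affected outputs are mITT and restricted mITT efficacy (SAP Table 15), NNT (Table 16), the sensitivity analyses (Table 17), the mITT subgroup analyses (SAP 8.2.1) and healthcare utilization, which SAP 8.2.3.3 runs in mITT.

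**Working it through.** **1. Apply each rule to one subject.** Take a vaccinated subject whose operation turns out to be a single-level fusion without multilevel instrumentation.

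| Rule | Result |
|---|---|
| Protocol 9.3.1, SAP 5.1 | In mITT efficacy: vaccinated and had spinal surgery |
| SAP 5.6.2(1) | Safety only: the planned index procedure was not done |
| SAP 5.5, term as defined in SAP 2.1 | Out of all efficacy analyses |
| SAP 5.5, term read as the operation performed | Not excluded |
| SAP 5.6.2(3c) | Out of per-protocol |

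Item 1 conflicts with 5.1. SAP 5.5 conflicts only on the narrow reading.

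**2. Which rule fits the rest of the plan?**

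- Item 3c would be largely redundant if item 1 had already sent these subjects to safety only.
- Protocol 6.1 keeps them in follow-up, so their endpoint data will exist.
- The log for Protocol Amendment 3, used here only as evidence of purpose, says that 9.3.1 was changed so that such subjects could enter an mITT population. The current text of 9.3.1 does that.

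All three point to 5.1 as the intended rule.

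**3. The other mITT sets.** SAP 5.4.1 (immunogenicity) requires vaccination and a valid post-vaccination result. SAP 5.4.2 (colonization) requires randomization and a valid swab result. Neither requires surgery. SAP 5.5 and 5.6.2(1) therefore conflict with these two definitions as well, even for subjects who have no operation at all.

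**4. Illustration of size.** SAP 8.1.1 gives VE = 1 − p/(1 − p), with p = x/n, x the SA4Ag cases and n all cases. The lower VE limit is 1 − pU/(1 − pU), where pU is the upper Clopper-Pearson limit for p.

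Check against the plan: for 14/48, VE = 1 − 14/34 = 58.8%. At 95.1%, pU = 0.4413 and the interval is 21.0% to 79.6%, which matches Protocol Table 15.

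SAP 8.1.1 evaluates mITT at two-sided 0.05, so the 95% level applies. Restoring a subject who is a case adds a case to n. Results below come from unrounded limits.

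| Split | VE | Lower 95% limit | Change |
|---|---|---|---|
| 14/48 | 1 − 14/34 = 58.8% | 21.2% | – |
| 15/49 (one SA4Ag case restored) | 1 − 15/34 = 55.9% | 16.8% | −4.4 points |
| 14/49 (one placebo case restored) | 1 − 14/35 = 60.0% | 23.7% | +2.5 points |

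The starting split is chosen for illustration. The documents do not say how many operated subjects had a non-index procedure, so no expected number of restored cases can be derived.

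**The case against.** The best defence is that both documents also use *index surgery* loosely, for whatever operation took place. Protocol 6.1 speaks of an index surgery not conducted according to the index definitions. SAP Section 7 says that vaccinated subjects without the index surgery have no Day 1 visit, which makes sense only if they had no operation. Item 3c itself supposes an index surgery that can fail the study criteria. This stands for SAP 5.5. A reader might infer that 5.5 flatly contradicts 5.1, but the documents support only ambiguity there.

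The defence does not carry over to 5.6.2(1), where the word *planned* ties the rule to the intended procedure. Taken literally, item 1 would even restrict to safety a subject who had a compliant multilevel fusion that departed from the recorded plan. That is hardly intended, but it is what the sentence says.

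Two further objections limit what may be concluded.

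- A reader might infer that mITT collapses into per-protocol and loses its purpose. It does not. Per-protocol also excludes for ineligibility, vaccination not as randomized, surgery outside 9 to 90 days, major deviations, and infection or malignancy found at surgery. mITT keeps those subjects. One criterion is duplicated.
- A reader might infer a shift of about 7 points at the efficacy boundary by comparing 14/48 with 15/48 at 95.1% (21.0% against 13.7%). That comparison swaps a placebo case for an SA4Ag case, and it uses the per-protocol confidence level. The 14-of-48 rule does not govern mITT. SAP 8.1.3.5 also records that the study met its futility criteria at the interim analysis and stopped enrolling, so a 48-case split is only an illustration here.

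**Conclusion.** Wrong as written. SAP 5.6.2(1) contradicts SAP 5.1 and Protocol 9.3.1, and 5.5 is ambiguous on the same point. The consequence is limited to the mITT and restricted mITT efficacy analyses with their NNT, sensitivity and subgroup versions, and to healthcare utilization. The immunogenicity and colonization sets have a separate mismatch with 5.4.1 and 5.4.2.

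The per-protocol primary analysis and the interim and futility rules are unaffected, because subjects with non-index surgery are outside per-protocol under either rule.

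The size depends on how many such subjects there are and which arm any cases among them belong to. The documents give neither, so bias in a particular direction cannot be claimed. The illustrated shifts of −4.4 and +2.5 points assume a 14/48 starting split and exactly one restored case.

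**What to change.** - In SAP 5.6.2(1) and 5.5, limit the exclusion to vaccinated subjects who undergo no spinal surgery, and state that it applies to the efficacy and healthcare-utilization analyses.
- Keep non-index surgery as a per-protocol-only exclusion under item 3c.
- Remove the restriction to the safety population from 5.6.2(1), and remove immunogenicity and colonization from the exclusion in 5.5, so that both agree with 5.4.1 and 5.4.2. Changing only the surgery wording would leave that second conflict in place.

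The cost is SAP wording. No new data, design change or protocol amendment is needed, since the change restores the rule already in Protocol 9.3.1.

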## 6. ENDPOINTS AND COVARIATES

### 6.1. Efficacy Endpoint(s)

All efficacy endpoint events will be evaluated by the EAC. The EAC will determine whether or not the event meets the case definition criteria, including diagnosis and onset date relative to surgery. Confirmed cases will contribute to the efficacy analyses.

Windows described as “within 90 days” (or “within 180 days”) mean that infections with onset occurring on Days 1-90 (or Days 1-180), inclusive, will be included. Day 1 is the day of the index surgery.

### **6.1.1. Primary Efficacy Endpoint**

*The number of subjects in each vaccine group with postoperative S aureus BSI and/or deep incisional or organ/space SSI occurring within 90 days of elective open posterior instrumented spinal fusion procedures with multilevel instrumentation, as confirmed by the EAC.*

### **6.1.2. Secondary Efficacy Endpoints**

- *The number of subjects in each vaccine group with postoperative S aureus BSI and/or deep incisional or organ/space SSI occurring within 180 days of elective open posterior instrumented spinal fusion procedures with multilevel instrumentation.*
- *The number of subjects in each vaccine group with postoperative S aureus SSI occurring within 90 days of elective open posterior instrumented spinal fusion procedures with multilevel instrumentation.*
- *The number of subjects in each vaccine group with postoperative S aureus SSI occurring within 180 days of elective open posterior instrumented spinal fusion procedures with multilevel instrumentation.*

### **6.1.3. Exploratory Endpoints**

- *The number of subjects in each vaccine group with postoperative ISA disease occurring within 90 days of elective open posterior instrumented spinal fusion procedures with multilevel instrumentation.*
- *The number of subjects in each vaccine group with postoperative ISA disease occurring within 180 days of elective open posterior instrumented spinal fusion procedures with multilevel instrumentation.*
- *The number of subjects in each vaccine group with postoperative S aureus BSI and/or deep incisional or organ/space SSI occurring within 90 days of elective open posterior instrumented spinal fusion procedures with multilevel instrumentation, based on baseline S aureus colonization status.*
- *The number of subjects in each vaccine group with postoperative S aureus BSI and/or deep incisional or organ/space SSI occurring within 180 days of elective open posterior instrumented spinal fusion procedures with multilevel instrumentation, based on baseline S aureus colonization status.*
- *The number of subjects in each vaccine group with postoperative BSI and/or deep incisional or organ/space SSI or superficial SSI, attributable to any pathogen, occurring within 90 days of elective open posterior instrumented spinal fusion procedures with multilevel instrumentation.*

- The number of subjects in each vaccine group with postoperative BSI and/or deep incisional or organ/space SSI or superficial SSI, attributable to any pathogen, occurring within 180 days of elective open posterior instrumented spinal fusion procedures with multilevel instrumentation.
- *The proportion of subjects at each time point who achieve specific antibody thresholds in antibody assays that assess functional activity. These may include, for example, opsonophagocytic activity (OPA) assays using an S aureus capsular polysaccharide serotype 5 (CP5)-expressing strain and a capsular polysaccharide serotype 8 (CP8)-expressing strain, and competitive Luminex immunoassays (cLIAs) for clumping factor A (ClfA) and manganese transporter C (MntC). Additional exploratory assays to measure immune responses may also be conducted on all 4 antigens.*
- *The proportion of subjects at each time point who achieve specific antibody thresholds to all 4 antigens both individually and combined using immunological assays.*
- *The number of subjects in each vaccine group determined to be colonized with S aureus on each occasion swab samples are collected.*
- *From subjects with S aureus infection, the association between S aureus strain or strains identified as colonizing the subject and the S aureus strain or strains recovered from the infection.*
- *Healthcare utilization data, including days in hospital, days in an intensive care unit (ICU), discharge disposition, inpatient days in rehabilitation facilities or skilled nursing facility after discharge, number of hospital readmissions and reoperations, days of antibiotic use, and number of rehabilitation/physical therapy outpatient visits.*

#### **6.1.4. Multiple Protocol-Defined Infections from the Same Subject**

If a subject has the same PDI more than once in a specified time window, then only the first occurrence will be included in the analysis.

A subject who has 1 infectious episode that worsens, eg, from superficial SSI to deep incisional or organ/space SSI or to BSI, will be counted in all endpoints for which he/she qualifies. However, no subject may be counted more than once in any endpoint analysis.

A subject may be included in more than 1 endpoint in a given time window. For example, a subject with BSI would be counted for both “BSI and/or deep incisional or organ/space SSI” and “ISA disease” endpoints.

A subject with 2 different PDIs in a specified time interval may be included in more than 1 endpoint analysis for that time interval. For example, a subject with superficial SSI within Days 1-90 and ISA disease within Days 91-180 would be included in 2 analyses for the Days 1-180 interval: “SSI occurring within 180 days” and “ISA disease within 180 days.”

Statistical methodology for efficacy is described in [Section 8.1.1](#).

## 6.2. Safety Endpoints

### 6.2.1. Adverse Events and Serious Adverse Events

AE analyses will be performed for the following intervals:

- From the day of vaccination until the day of surgery
- From the day of vaccination until the Day 42 postoperative evaluation
- From the day of surgery until the Day 42 postoperative evaluation
- From the Day 42 postoperative evaluation until the Day 180 postoperative evaluation (newly diagnosed chronic medical disorders only)

Analyses for serious adverse events (SAEs) and deaths will be performed for the following intervals:

- From vaccination until the day of surgery
- From vaccination until the Day 180 postoperative evaluation
- From the day of surgery until the Day 180 postoperative evaluation

Deaths will be categorized as associated with *S aureus* infection or not associated with *S aureus* infection.

Statistical methodology for AEs is described in [Section 8.1.2.1](#).

### 6.2.2. Multiple-Organ Failures

Each multiple-organ failure (MOF) will be classified as an AE or SAE and so appear in the appropriate analysis. However, other MOF endpoints will also be examined:

- Number and proportion of subjects with organ system failure by organ (eg, renal, hepatic, pulmonary). By definition of MOF, each subject will be included in analyses of more than 1 organ.
- Number and proportion of subjects who meet the criteria for MOF.
- Among subjects with MOF, the number and proportion associated with PDI, non-PDI (other infection), other (not an infection), or unknown. More than 1 category may be selected.
- Among subjects with MOF that is associated with PDI or non-PDI, whether the infection is microbiologically confirmed *S aureus*, microbiologically confirmed non-*S aureus*, or not microbiologically confirmed.

Statistical methodology for MOF is described in [Section 8.1.2.2](#).

**6.2.3. Local Reactions and Systemic Events**

Day 1 is defined in this study as the day of the index surgery. References to “Days 1-10” in this section refer to the 10 days following vaccination.

The grading scales for local reactions and systemic events are derived from the Food and Drug Administration (FDA) Center for Biologics Evaluation and Research (CBER) guidelines on toxicity grading scales for healthy adult volunteers enrolled in preventive vaccine clinical trials.

Subjects will assess redness, swelling, and pain at the site of vaccination and record the symptoms in the electronic diary (e-diary) for 10 consecutive days starting on the day of vaccination. Redness and swelling will be measured and recorded in caliper units (range: 1 to 21+), and then categorized as mild, moderate, or severe based on the grading scale in Table 2.

**Table 2. Local Reaction Grading Scale**

	GRADE 1 Mild	GRADE 2 Moderate	GRADE 3a Severe	GRADE 4b
Redness	5 to 10 caliper units (or measuring device units) 2.5 to 5.0 cm	11 to 20 caliper units (or measuring device units) 5.5 to 10.0 cm	≥21 caliper units (or measuring device units) ≥10.5 cm	Necrosis or exfoliative dermatitis b
Swelling	5 to 10 caliper units (or measuring device units) 2.5 to 5.0 cm	11 to 20 caliper units (or measuring device units) 5.5 to 10.0 cm	≥21 caliper units (or measuring device units) ≥10.5 cm	Necrosis b
Pain at injection site	Does not interfere with activity	Interferes with activity	Prevents daily activity	Emergency room visit or hospitalization

a. Subjects experiencing local reactions ≥21 caliper units (≥10.5 cm) will telephone the study site. In the event that the subject does not call, the investigator will call the subject.

b. Grade 4 assessment should be made by the investigator and recorded as an AE on the case report form.

Note: If the size of the redness and/or swelling falls between 2 caliper units, the higher caliper unit number will be recorded in the electronic diary (e-diary).

Numeric scores for the local reactions will be: none = 0, mild = 1, moderate = 2, and severe = 3.

Grade 4 will not be collected in the e-diary. Only an investigator is able to classify a subject’s local reaction as Grade 4, after physical examination of the subject or telephone contact with the subject. Any such local reactions will be recorded as AE on the CRF. In addition to their inclusion in the general AE analysis, these events will be listed and discussed separately as reactogenicity events.

The derived local reaction variables are:

1. Maximum grade during Days 1-10 after vaccination, for each local reaction.

2. Mild, moderate, or severe response during Days 1-10 after vaccination, for each local reaction.
3. Duration in days, but not for “any local reaction.”
4. Onset of the indicated local reaction in days.
5. Onset of “any local reaction” in days.

The mild, moderate, or severe response during Days 1-10 after vaccination is “yes” if present on at least 1 day.

A given local reaction is “yes” for Days 1-10 after vaccination if present on at least 1 day, is “no” if the subject reports any combination of “no” and “missing” on each of Days 1-10 after vaccination, and is “missing” if every day is missing.

“Any local reaction” is “yes” for Days 1-10 after vaccination if at least 1 local reaction is present on at least 1 day, is “no” if the subject reports “no” or missing for every local reaction on each of Days 1-10 after vaccination, and is “missing” if every local reaction on every day is missing.

Duration of local reaction is calculated as the date of the last reported reaction minus the date of the first reported reaction, plus 1. If the local reaction has not resolved by the last date in the e-diary, then the resolution date recorded in the case report form (CRF) will serve as the date of the last reported reaction. If the resolution date is missing from the CRF, then duration will be set to missing. Duration will be missing for subjects without the indicated local reaction. Duration will not be calculated for “any local reaction.”

The onset day for a local reaction is the first day of the reaction, even if the reaction later becomes more severe. The onset day for “any local reaction” will be the first day of any local reaction, regardless of severity. Onset day will be missing for subjects without the indicated local reaction.

Local reactions recorded on or after the day of surgery will be excluded from all analyses.

Numeric scores for the systemic events are the same as for local reactions: none = 0, mild = 1, moderate = 2, and severe = 3. The systemic event grading scale is presented in Table 3.

